5.8.3. REPLACEMENT STRATEGY

No replacement of patient is foreseen.

5.9. DISCONTINUATION OF STUDY SITE

Study site participation may be discontinued if the Sponsor, the Investigator, or the EC of the study site judges it necessary for any reason.

5.10. DISCONTINUATION OF PATIENT'S PARTICIPATION

The criteria for enrolment should be followed explicitly. If a patient who does not meet enrolment criteria is inadvertently enrolled in the study, that patient should be discontinued from the study, and the Sponsor must be informed.

5.11. DISCONTINUATION OF STUDY

The study can be discontinued prematurely at any time if the Sponsor judges it necessary for any reason. In that case, all scheduled procedures and/or procedures of early discontinuation phone call will be performed.

6. STUDY TREATMENT

6.1. STUDY DRUG AND TREATMENT OF PATIENTS

No IMP will be administered in this observational study.

Patients will be treated by the Investigator for pain relief exactly as they would normally be based on their needs and clinician practice.

6.1.1. INVESTIGATIONAL DRUG FORMULATION(S)

Not applicable.

6.1.2. SUPPLIES, PACKAGING, LABELING, ACCOUNTABILITY AND STORAGE

Not applicable.

6.1.3. STUDY DRUG ADMINISTRATION

Not applicable.

6.2. BLINDING MAINTENANCE / UNBLINDING

Not applicable.

6.3. CONCOMITANT THERAPY

Patients will take their analgesic treatment as prescribed by the Investigator. Drug therapy for cancer will be continued following patient needs.

See section 7.2.2 for supplemental rescue analgesic medication information.

All analgesic medication taken over the last month preceding enrolment and primary disease medication will be recorded on the Case Report Form (CRF). Any investigational drug taken over the previous year will also be recorded.

6.4. PRODUCT COMPLAINT

Not applicable.

7. PATIENT MANAGEMENT AND INSTRUCTIONS

7.1. STUDY PATIENT MANAGEMENT AND REQUIREMENTS

The patients will be required to attend the Investigator site at the following occasions: at screening/enrolment, Visit 2, optional Visit 1B and intermediate evaluation Visit. The patients will be discharged from the study at Visit 2.

Throughout the study, patients may undergo medical assessments and review of compliance with restrictions before continuing in the study.

7.2. STUDY RESTRICTIONS

7.2.1. STUDY DRUG ADMINISTRATION

No investigational drug will be administered to patients during this study. The Investigator will prescribe analgesic treatment to patients based upon their regular practice.

7.2.2. OTHER RESTRICTIONS

Medications

During the study and in addition to their current analgesic treatment, patients will be permitted to supplement their analgesic treatment with rescue analgesic drugs (named rescue medication). Type and dose regimen of these rescue medications will be left at the discretion of Investigator.

7.2.2.1. Diary

Once a day from enrolment till Visit 2, approximately at the same time of the day in the evening, patients will complete their diary.

The following data will be recorded:

- pain intensity assessment by recording APS and WPS for the last 24 hours (from enrolment till Visit 2 or early discontinuation). See Sections 8.2.4.4 and 8.2.4.5 for further description of APS and WPS,
- any potential event that may help to understand unexpected study outcomes,
- intake of rescue analgesic treatment if any (from enrolment to Visit 2 or early discontinuation).

8. STUDY ASSESSMENTS

Timing of assessments is specified in Sections 16.1 and 16.2 Study Schedule.

8.1. PHARMACOKINETICS ASSESSMENT

Not applicable.

8.2. PHARMACODYNAMIC ASSESSMENTS

8.2.1. CLINICAL PAIN ASSESSMENTS (CPAs)

The following CPAs will be performed at enrolment, at Visit 2 and at optional intermediate evaluation Visit as specified in Sections 16.1 and 16.2 Study Schedule.

First, the painful areas (PA) will be defined by patients, using a standardized blank body map. CPAs will then be carried out by the Investigator or his/her designee on the skin overlying the most painful area (MPA) reported by the patient. The control area to compare to would be the equivalent dermatome region on the contralateral side of the body, or for central spinal sites an alternative non-painful area at the spinal level. This control area site will be defined as “normal”.

If the MPA is different at the next visit from the previous one, all assessments will be performed on the current MPA first and then again on the previous visit MPA. However, in the case scenario of the MPA at Visit 2 is different from both the one identified at intermediate evaluation Visit and the other at enrolment, only MPA defined as such at previous visit (intermediate evaluation) and at this current Visit 2 will be assessed.

Regarding MPA, clinical signs are identified as follows:

- Hypoesthesia is defined as the presence of an area where light touch of the blunt end of a paintbrush is felt less precisely than in referent control areas.
- Sensory loss is defined as the presence of an area where the same light touch as referred above is not felt at all.
- Hyperalgesia is defined as the presence of an area where the pain induced by stimulus applied perpendicularly to the skin is felt abnormally intensely.
- Allodynia is defined as the presence of an area of pain after the application of non-painful stimulus.

The centre of an area with allodynia or hyperalgesia is considered for further evaluation. However, in the absence of allodynia and hyperalgesia the centre of the area of hypoesthesia or sensory loss is then considered.

All CPAs will be carried out in a quiet environment, with a relaxed patient, previously instructed on the procedure. If a test provoked pain, the Investigator will wait for pain disappearance before proceeding with the next test. All CPAs will be completed within approximately 20 minutes.

The CPAs will include the following parameters:

The Most Painful Area (MPA)

The MPA will be mapped on a standardized body map. The area with abnormal sensation will be delimited with a dermatographic pencil and a picture of it will be taken in such a way the MPA surface can be calculated. Patient identity must always be concealed when taking the photography. Further instructions will be given in a dedicated manual.

Static Allodynia (SA)

SA will be assessed using a standardized calibrated von Frey hair number 13 (5,1g) (or equivalent device) at the centre of both painful and control areas. The patient will be asked to describe this sensation compared with the control area (hyperesthesia, hypoesthesia or unchanged) and, if painful, to rate the pain on an 11-point NRS.

Dynamic Mechanical Allodynia (DMA)

DMA will be assessed using a standardized calibrated brush (SENSELab Brush-05, Somedic or equivalent device). 3 successive gentle strokes will be performed over a 40mm length of skin bilaterally at interval of 1 second interval. The patient will be asked to describe this sensation compared with the control area (hyperesthesia, hypoesthesia or unchanged) and, if painful, to rate the pain on an 11-point NRS.

Mechanical Pain Threshold (MPT)

MPT will be assessed with a series of 7 von Frey monofilaments (SENSELab von Frey Aesthesiometer II, Somedic or equivalent device) of varying thickness, calibrated according to the force required to make them bend. The force of the stimulus becoming painful is recorded. This assessment is conducted one time on the control area but repeated 3 times on the affected area. Suprathreshold level may be measured in both the control area and affected area using the strongest von Frey hair number 16 and will be rated with an 11-point NRS.

Thermal Pain Sensitivity (TPS)

Responses to heat at 40 °C (H-TPS) and cool at 25°C (C-TPS) will be examined using thermal rollers (Rolltemp, Somedic or equivalent device) in both the affected and control areas. The presence of hyperesthesia or hypoesthesia or thermal allodynia will be recorded and rated on an 11-point NRS if painful. Responses will be recorded as increased, reduced or equivalent sensation compared to the control area.

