2.3. SECONDARY ENDPOINTS

Individual analgesic treatment efficacy outcomes:

- Patient's change from baseline of pain severity, as measured by the weekly means of the daily Worst Pain Score (WPS),
- Patient's change from baseline of pain severity and interference as measured by the Brief Pain Inventory (BPI),
- Patient's change from baseline of Investigator and Patient Global Assessment of Changes (IGAC and PGAC),
- Patient's change from baseline of pain intensity measured after Clinical Pain Assessments (CPAs) at Visit 2.
- Patient's change from baseline of Quality-of-Life Questionnaire in 30 questions (QLQ-C30).

Endpoints used for the predictive factors (independent variables).

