4.1.2. OBSERVATIONAL PERIOD – INTERMEDIATE PHONE CALL

The observational period is a 4- to 10-week analgesic treatment therapy period including a phone call scheduled approximately 2 weeks after Visit 1 or Visit 1B (See figure 1. Study Diagram).

During this phone call, the Investigator site staff will inquire about patient general health status and pain relief. The patient will be reminded about Visit 2 scheduled date, diary and prescribed analgesic treatment compliance. At the end of the phone call, an intermediate visit to Investigator site may be organized within the next days at the discretion of Investigator.

If organized, this visit will start with collection of the diary, checking compliance to diary completion instructions and to prescribed analgesic treatment. Patient will complete BPI and go through all CPAs. At the end of this optional visit, the Investigator will review the analgesic treatment. Patients will continue to complete a diary up to Visit 2.

For a complete list of assessments to be performed at Intermediate Evaluation Visit, see Study Schedule Sections 16.1. and 16.2. This optional visit is also depicted in Figure 4.

At this visit, patients will remain at the Investigator site for approximately 1 hour.

[figure not shown]

[figure not shown]
Figure 4. Sequence of Assessments at Intermediate Evaluation Visit

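### The Visit 2 CPA retest is tied to the previous visit's painful area, so some patients with an intermediate visit have no same-site change from enrolment

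*Protocol*

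**What the plan says.** Protocol Section 2.3 lists as a secondary endpoint the "change from baseline of pain intensity measured after Clinical Pain Assessments (CPAs) at Visit 2". The Synopsis plans the comparison between the enrolment visit and Visit 2. Protocol Section 10.1.1.1 and SAP Section 2.5 carry the same change from baseline, and none of these places names a body site.

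Protocol Section 8.2.1 sets the site. CPAs are done on the MPA that the patient reports at that visit. If it differs from the one at the previous visit, "all assessments will be performed on the current MPA first and then again on the previous visit MPA". An exception follows for the case where the "MPA at Visit 2 is different from both the one identified at intermediate evaluation Visit and the other at enrolment": then "only MPA defined as such at previous visit (intermediate evaluation) and at this current Visit 2 will be assessed".

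The intermediate visit is optional. Under Protocol Section 4.1.2, after the phone call an "intermediate visit to Investigator site may be organized within the next days at the discretion of Investigator". CPAs are part of it: "Patient will complete BPI and go through all CPAs". For a patient who has this visit, the previous visit at Visit 2 is therefore the intermediate one, not enrolment.

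SAP Section 4.2 lists CPA as measured at V1 and V2. CPA is not among the variables taken from the diary and the intermediate visit.

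**The concern.** The endpoint looks back to enrolment, while the retest rule looks back one visit. The two coincide only when there is no intermediate visit or the MPA has not moved by then. Otherwise the enrolment area can go untested at Visit 2, while the areas that are tested then have no enrolment value.

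The measures are local. Filament thresholds, evoked pain ratings and thermal responses are taken at the painful area and judged against a control area chosen for it. A difference between two body sites mixes location with change over time. At stake is whether a named secondary endpoint exists for these patients and, if an analyst computes it anyway, what it means.

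**Working it through.** No sample size, power or alpha is involved, so there is no figure of the plan to reproduce. The check is to apply Section 8.2.1 literally to every possible path of the MPA. Call the enrolment area A, and later new areas B and C.

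| Enrolment – intermediate – Visit 2 | Tested at Visit 2 | A retested? |
|---|---|---|
| A – no visit – A | A | yes |
| A – no visit – B | B, A | yes |
| A – A – A | A | yes |
| A – A – B | B, A | yes |
| A – B – A | A, B | yes |
| A – B – B | B | no |
| A – B – C | C, B | no |

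The enrolment area is retested in 5 of 7 paths and missed in 2. A-B-C fails by the express words of the exception. A-B-B fails by the general rule: the Visit 2 area equals the previous visit's area, so nothing triggers a second site. In A-B-A the enrolment area is tested because it is again the current MPA.

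In both failing paths A was retested at the intermediate visit. A same-site change to that visit exists, but it is not the Visit 2 endpoint.

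If Visit 2 always covered the current MPA and the enrolment MPA, all 7 paths would have a same-site pair, with at most two areas tested.

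**Size.** The documents give no rates, so three quantities are assumed:
- q, the share of completers who have the intermediate visit: 0.25 to 1
- m, the probability that the MPA has moved by then: 0.1 to 0.3
- r, the probability that it is back at A by Visit 2, given that it moved: 0 to 0.5

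With about 140 planned completers (Protocol Section 4.2.1), affected = 140 × q × m × (1 − r).
- Low: 140 × 0.25 × 0.1 × 0.5 = 1.75, about 2
- Middle: 140 × 0.5 × 0.2 × 0.75 = 10.5
- High: 140 × 1 × 0.3 × 1 = 42

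These figures count A-B-B and A-B-C together. If only A-B-C fails, they must be multiplied by the share of these patients who moved again to a third area. That share is also unknown, so the number would be smaller.

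**The case against.** **The A-B-B case is open to argument.** If the general rule reaches back only one visit, it already yields C and B in the three-site case, and the exception adds nothing. An exception that restricts something makes sense only if the general rule was meant to reach earlier areas, including enrolment. On that reading A-B-B would test B and then A, and only A-B-C would fail. This stands as an ambiguity. The literal wording favours the failing result, but a reader should not infer that a single lasting move certainly loses the enrolment area.

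**A same-site change is nowhere required.** One could define the endpoint as change at whichever area is currently worst, which can be computed in every path. No section states that definition, however. It also fits poorly with a protocol that retests earlier areas and uses site-specific thresholds and controls. What stands is that the SAP leaves the choice of area open, so changing the retest rule alone would not settle the matter.

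**The consequences are limited.** This is right. The endpoint is secondary, SAP Section 5 specifies no analysis of CPA change, and the correlation of APS with CPA at Visits 1 and 2 needs no site pairing.

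**Informative loss is conjecture.** A reader might infer that patients with worse or changing pain lose the endpoint selectively, because the optional visit follows a call about health status and pain relief. The documents tie the visit only to the Investigator's discretion and do not link a move of the MPA to response. The loss may depend on pain course, but need not.

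**Conclusion.** The retest rule and the endpoint do not match. For A-B-C the text is express: the enrolment area has no Visit 2 value. For A-B-B the same follows from the literal rule, with the ambiguity noted. In either path no same-site change from enrolment to Visit 2 exists, and neither document says what is to be analysed instead. In A-B-C the rule keeps the intermediate area, which feeds no planned endpoint, and drops the one that the endpoint needs.

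It would be too strong to say that the baseline area is lost whenever the MPA has moved by the intermediate visit, since A-B-A is safe. Patients without that visit always have the enrolment area retested. The number affected is unknown. The range of about 2 to 42 of 140 rests wholly on the assumed q, m and r and on counting both failing paths. The conclusion itself depends on none of these. The primary APS endpoint is unaffected. This is worth correcting as a defect of a secondary endpoint, but it does not threaten the study's main result.

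**What to change.** In Protocol Section 8.2.1 and the dedicated manual that it mentions, anchor the rule to baseline: at Visit 2, CPAs are done on the current MPA and, if different, on the enrolment MPA. In the SAP, state that CPA change from baseline uses the enrolment MPA, and how patients without a same-site pair are handled. Patients who have already completed without such a pair should be flagged and not analysed as cross-site changes.

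Costs:
- A-B-C: still two areas, but the intermediate area is no longer followed to Visit 2.
- A-B-A: one set fewer, with the same loss of follow-up of the intermediate area. No planned endpoint uses that follow-up.
- A-B-B: one extra CPA set of about 20 minutes, in a visit planned at about one hour.
- The amendment goes to the ethics committees (Protocol Section 11.2). The SAP is dated April 2017 with the interim transfer estimated for May 2017, so a change at that point would leave data collected under two rules. The SAP statement and the flag are needed whether or not the protocol is amended.

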8.2.2. PERSONALITY EVALUATIONS

The following personality questionnaires will be collected at the times specified in Sections 16.1 and 16.2 Study Schedule.

8.2.2.1. Multidimensional Health Locus of Control Scale (MHLCS)

Pain perception may be related to patient perceptions of control of life event. The MHLCS classify patients within 2 categories: patients with internal locus of control, who believe that their life events are controlled by themselves, patients with external locus of control who believe that their life events are controlled by factors such as luck or fate and

patients with external locus of control who believe that their life events are controlled by powerful others (such as health professionals, relatives and some other people). The MHLCS consists of 18 self-report items with a rating ranging from 1 (strongly disagree) to 4 (strongly agree) (Wallston et al. 1978).

8.2.2.2. Hospital Anxiety and Depression Scale (HADS)

The depression and the anxiety scale of the HADS consist of 14 items, which are rated on a 4-point scale (Zigmond and Snaith 1983).

8.2.2.3. Revised Life Orientation Test (LOT-R)

The LOT-R is an improved version of the original Life Orientation Test (LOT) and it defines optimism-pessimism as generalized positive and negative outcome expectancies. The LOT-R consists of 6 self-report items and 4 filler items. Each item is rated on a 5-point scale ranging from 0 (strongly disagree) to 4 (strongly agree). To calculate optimism-pessimism scores, the three pessimism items (e.g. I hardly ever expect things to go my way) are reverse coded and added to the three optimism items (e.g., In uncertain times, I usually expect the best) to create a summary optimism-pessimism score (Scheier et al. 1994).

8.2.2.4. Expectation Questionnaire

Directed expectancy is measured by asking the patients: “How much do you expect this analgesic treatment will change your current pain?”

Similarly, the desire for pain relief is measured by asking the patients “How strong is your desire to find an analgesic treatment relieving you from pain?”

The ratings will be reported using an 11-point NRS ranging from 0 (not at all) to 10 (as best as possible).

8.2.3. PAIN DISEASE EVALUATION

The following evaluations will be collected at the times specified in Sections 16.1 and 16.2 Study Schedule.

8.2.3.1. DN4 Questionnaire (DN4)

“Douleur Neuropathique en 4 questions” (DN4) questionnaire is a clinician-administered questionnaire including both items related to the interview (i.e. symptoms) and items related to the sensory examination (i.e. signs) (Bouhassira et al. 2005).

It consists of 7 dichotomous questions (yes/no) related to the painful area from interview of the patient (burning, painful cold, electric shocks, tingling, pins and needles, numbness and itching) and of 3 items (yes/no) related to the physical examination in the PA (hypoesthesia to touch, hypoesthesia to prick and pain caused or increased by brushing).

Pain is considered as neuropathic if the DN4 score is ≥ 4 .

8.2.3.2. Neuropathic Pain Symptom Inventory (NPSI)

The NPSI is a self-administered questionnaire that includes 10 pain descriptors of intensity and 2 temporal items (Bouhassira et al. 2004). The intensity of pain is rated on an 11-point NRS. The 10 pain descriptors of the NPSI pertain to 5 distinct clinically relevant dimensions: spontaneous burning pain, spontaneous deep pain, paroxysmal pain, evoked pain, and paresthesia/dysesthesia. The scoring of the NPSI includes both a total score of neuropathic symptoms intensity and 5 sub-scores. Temporal items are designed to assess spontaneous ongoing pain duration and the number of pain paroxysms over 24 hours.

8.2.3.3. Pain Catastrophizing Scales (PCS)

Catastrophizing thoughts concerning pain are measured with the PCS (Sullivan et al. 1995). It consists of 13 items that are answered on a 5-point scale ranging from 0 (not at all) to 4 (all the time). The subscale “Rumination” describes the inability to stop thoughts concerning pain. The subscale “Magnification” reflects the tendency to exaggerate the threat value of pain stimuli. The subscale “Helplessness” describes the feeling of inability to deal with the pain. The PCS total score is calculated by summing up all the items.

8.2.4. PAIN EVALUATIONS

The following pain evaluations will be collected at the times specified in Sections 16.1 and 16.2 Study Schedule.

8.2.4.1. Brief Pain Inventory (BPI) Short Form

BPI is a self-reported scale that measures the severity of pain and the interference of pain on function (Charles S. Cleeland © 2009). In the short form of BPI, there are 4 questions assessing worst pain, least pain, actual pain and average pain in the past 24 hours. The severity scores range from 0 (no pain) to 10 (pain as bad as you can imagine). There are 7 questions assessing the interference of pain in the past 24 hours for general activity, mood, walking ability, normal work, relation to other people, sleep and enjoyment of life. The interference scores range from 0 (does not interfere) to 10 (completely interferes).

8.2.4.2. Investigator Global Assessment of Changes (IGAC)

The IGAC is a subjective evaluation using a NRS to answer the following question: “If you take into consideration all the various ways the pain influence the patient and his/her life, how do you then evaluate the patient’s condition today?” with 0 meaning “best” and 10 “worst”.

8.2.4.3. Patient Global Assessment of Changes (PGAC)

PGAC is a subjective evaluation using a NRS to answer the following question: “If you take into consideration all the various ways the pain influence you and your life how do you then evaluate your condition over the last week?” with 0 meaning “very good” and 10 meaning “very bad”.

8.2.4.4. Average Pain Score (APS)

The APS will measure the average pain intensity over the last 24 hours by asking the patient “Could you please indicate us how was your average pain during the last 24 hours? For this, circle the most descriptive number on this scale.” The patient will be asked to rate it on an 11-point NRS ranging from 0 (no pain) to 10 (pain as bad as you can imagine). However, before being enrolled into the study, the patient will be asked an APS over the past week (WAPS).

8.2.4.5. Worst Pain Score (WPS):

The WPS will measure the worst pain intensity over the last 24 hours by asking the patient “Could you please indicate us how was your worst pain during the last 24 hours? For this, circle the most descriptive number on this scale.” The patient will be asked to rate it on an 11-point NRS ranging from 0 (no pain) to 10 (pain as bad as you can imagine).

